4. STUDY DESIGN

4.1. Overall design

- Study 219575 is a Phase 3b, open-label, single-arm, multicenter study to evaluate clinical symptom improvement and the safety of gepotidacin during the treatment of uUTIs.
- Female participants ≥ 12 years of age with 2 or more clinical symptoms of uUTI and nitrite or pyuria from a pretreatment clean-catch midstream urine sample will be offered enrollment into the study and consented/assented (Section 5.1). Participants who meet eligibility requirements will receive gepotidacin 1500 mg administered orally BID for 5 days. (Note: Each dose is to be taken after food consumption and with water to assist with tolerability.)
- Appropriate clinical symptom and safety assessments will be conducted throughout the study. The total duration of study participation is approximately 28 days, with at least 1 planned onsite study visit and 6 telephone call study contacts (see Section 1.3 and Section 8 for study visit details), with allowance for unscheduled visits, as follows:
 - Visit 1 (Baseline/Day 1): onsite
 - Visit 2 (24 hours ± 4 hours), Visit 3 (48 hours ± 4 hours), Visit 4 (72 hours ± 4 hours), and Visit 5 (96 hours ± 4 hours): telephone
 - Visit 6 [REDACTED]: telephone
 - Visit 7 (Follow-up/Day 28): telephone
 - Unscheduled Visit: onsite or telephone
 - An additional onsite or telephone visit will be arranged if there are safety concerns, lack of response to study intervention, or early withdrawal.
- Note: Each visit will be assessed over a 24-hour period, starting with the first dose of study intervention received for an individual participant. For example, participants who only receive 1 dose of study intervention on their first calendar day in the study due to a late afternoon/evening Baseline Visit will take the second dose on the following calendar day, which will complete Visit 1. This pattern will continue until all 10 doses are received; thus, the tenth/last dose will be taken prior to Visit 5 (96 hours ± 4 hours) (may be 5 or 6 calendar days, depending on when the first dose is taken).
- The study is outsourced and PPD will perform all study-related activities on behalf of GSK. PPD MedCom will perform activities completed by Virtual Research Coordination Center during the study.

CCI

- [REDACTED]

- Refer to Appendix Section 10.11 for details regarding allowed revisions to monitoring due to the coronavirus disease.
- The primary uUTI symptom assessment will be the CSS (Appendix Section 10.1) at Visit 2 (24 hours \pm 4 hours). Participants must have taken a total of 2 doses of gepotidacin before the Visit 2 (24 hours \pm 4 hours) assessment of CSS. For the primary endpoint, clinical symptom improvement is defined as a decrease from Baseline of \geq 1 point in the CSS total score 24 hours (\pm 4 hours) after starting gepotidacin.
- Other uUTI assessments will include the CCI [REDACTED] (Appendix Section 10.2).
CCI
[REDACTED]

A study design schematic is provided in Section 1.2. The SoA is provided in Section 1.3.

Collection of study information via telemedicine during unexpected circumstances will be performed as local regulations permit.

Participant safety will be monitored by the medical monitor, designated safety lead (or delegate), and a GSK SRT throughout the study (Section 8.3.6).

4.2. Scientific rationale for study design

uUTIs affect the quality of life of patients. Feedback from patients and medical providers has demonstrated the need to better assess the burden of UTIs in women and early clinical symptom improvement on a daily basis.

The Phase 3 gepotidacin studies conducted in uUTI (Section 2.2) were conducted based on the need to identify new and effective oral antibiotic treatment options for uUTI, as such therapies are becoming limited due to the increase of MDR uropathogens and ESBL-producing Enterobacterales uropathogens, which are impacting the efficacy of the currently available oral antibacterial treatment options. The studies focused on a primary therapeutic response composite endpoint of both clinical resolution and microbiological eradication, which were measured at specific time points, in line with regulatory guidance [DHHS, 2019].

However, the Phase 3 studies did not measure symptom improvement on a daily basis after the start of study intervention to characterize the time profile of change in clinical symptomatology improvement. The present study will align with the study design and treatment aspects of the gepotidacin Phase 3 studies [Perry, 2022]; however, it will focus primarily on clinical symptom improvement in participants with a uUTI by assessing the CSS on a daily basis after the start of and during gepotidacin treatment. This study data will provide additional clinical data for gepotidacin in uUTIs.

4.3. Justification for dose

The oral gepotidacin dose in this study is 1500 mg BID (total daily dose of 3000 mg) for 5 days. This dosing regimen is the same as evaluated in a Phase 2 uUTI study and the Phase 3 uUTI studies conducted for gepotidacin (Section 2.2) [Perry, 2022]. This dose is justified because it supports the PK attainment targets for gepotidacin against uUTI uropathogens [Scangarella-Oman, 2022] and resulted in achieving noninferiority (Study 204989) and both noninferiority and superiority (Study 212390) results based on therapeutic response at the interim analysis when compared with the nitrofurantoin current first-line agent for efficacious antibacterial treatment of uUTI in women [Gupta, 2011; NICE, 2019; EAU, 2019; Hall, 2023].

4.4. End-of-study definition

A participant is considered to have completed study intervention if the participant has taken all doses of the study intervention (1500 mg BID taken as 2 × 750 mg tablets for a total of 10 doses). A participant is considered to have completed the study if the participant has completed all study visits including Visit 7 (Follow-up/Day 28).

The end of the study is defined as the date of the last visit of the last participant in the study.

5. STUDY POPULATION

Prospective approval of protocol deviations to recruitment and enrollment criteria, also known as protocol waivers or exemptions, is not permitted.

5.1. Inclusion criteria

Participants are eligible to be included in the study only if all of the following criteria apply:

Age and weight

1. The participant is ≥ 12 years of age at the time of signing the ICF/IAF and has a body weight ≥ 40 kg.

Note: Although participants as young as 12 years of age may enroll in the study, study sites must follow their IRB guidelines. Enrollment will be contingent upon such approvals regarding the allowed lower age limit for clinical study participants.

Type of participant and disease characteristics

2. The participant has 2 or more of the following clinical symptoms of uUTI with onset <96 hours prior to study entry: dysuria, frequency, urgency, or lower abdominal pain based on investigator assessment (see Appendix Section 10.1).
3. The participant has nitrite or pyuria (presence of 3+/large leukocyte esterase) from a pretreatment clean-catch midstream urine sample per local laboratory procedures.

Sex

4. The participant is female.

Contraceptive use is to be consistent with local regulations regarding the methods of contraception for those participating in clinical studies.

- A female participant is eligible to participate if she is a WOCBP who is not pregnant as confirmed by a high sensitivity urine pregnancy test predose at baseline regardless of current or prior contraception use or abstinence, is not breastfeeding, or is not a WOCBP as defined in Appendix Section 10.3.1.2.

Note: Collection of pregnancy information, contraceptive guidance, and WOCBP definitions are provided in Appendix Section 10.3, and requirements for pregnancy testing during and after study intervention are located in Appendix Section 10.7.

- The investigator is responsible for review of medical history, menstrual history, and recent sexual activity to decrease the risk for inclusion of a woman with an early undetected pregnancy.

Informed consent

5. The participant is capable of giving documented informed consent/assent as described in Appendix Section 10.9.3, which includes compliance with the requirements and restrictions listed in the ICF/IAF and in this protocol.

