Use in participants with renal dysfunction	A substantial increase in Cmax and AUC and decrease in clearance was observed in severe renal impairment/ESRD participants not on hemodialysis and in ESRD participants requiring hemodialysis (note: gepotidacin may have been administered at any time other than when receiving dialysis).	Specific exclusion criteria related to renal conditions and laboratory results have been implemented in the protocol.

CONFIDENTIAL

219575
Protocol Amendment 1 Final

Potential Risk of Clinical Significance	Summary of Data/Rationale for Risk	Mitigation Strategy

Reproductive System Effects
 
Preclinical studies demonstrated that gepotidacin was not genotoxic and no drug-related malformations were observed. Although positive in vitro findings for clastogenicity, consistent with a mechanism related to mammalian topoisomerase II inhibition were found, in vivo data from rat micronucleus and COMET assays suggest that gepotidacin does not pose a genotoxic hazard to humans.
 
Gepotidacin effects on embryofetal development were limited to decreased fetal weights for male and female fetuses in rats and decreased fetal weights and increased fetal resorptions (fetal deaths) in mice, both at maternally toxic doses. These occurred at clinically relevant exposures (65 µg.h/mL in rat and 35 µg.h/mL in mouse).
	
There are no data on the use of gepotidacin in pregnant women.
	
Gepotidacin is not recommended in pregnant or nursing mothers. Pregnancy testing requirements in this study minimize the risk of exposure to a fetus. See Appendix Section 10.3 for contraceptive measures and for required pregnancy testing.

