10.3. Appendix 3: Contraceptive and barrier guidance

10.3.1. Definitions

10.3.1.1. Woman of childbearing potential (WOCBP)

Women in the following categories are considered WOCBP (fertile):

- Adolescents of childbearing potential: Tanner stage ≥ 2 (post-thelarche) irrespective of the occurrence of menarche or following menarche.
- From the time of menarche until becoming postmenopausal unless permanently sterile (see below).

Note: Menarche is the first onset of menses in a young female. Menarche is normally preceded by several changes associated with puberty, including breast development and pubic hair growth.

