10.3.1.2. Woman of nonchildbearing potential (WONCBP)

Women in the following categories are considered WONCBP:

1. Premenarchal: Tanner stage 1 (prepubertal)
2. Permanently sterile due to one of the following procedures:
 - Documented hysterectomy
 - Documented bilateral salpingectomy
 - Documented bilateral oophorectomy
 - For permanently sterile individuals due to an alternate medical cause other than the above (e.g., Mullerian agenesis, androgen insensitivity, gonadal dysgenesis), investigator discretion will be applied to determining study entry. If reproductive status is questionable, additional evaluations are to be considered.

Note: Documentation can come from the site personnel's review of the participant's medical records, medical examination, or medical history interview.

3. Postmenopausal female
 - A postmenopausal state is defined as no menses for 12 months without an alternative medical cause. A high FSH level in the postmenopausal range may be used to confirm a postmenopausal state in women not using hormonal contraception or HRT. However, in the absence of 12 months of amenorrhea, confirmation with more than one FSH measurement is required.
 - Females on HRT and whose menopausal status is in doubt must discontinue HRT to allow confirmation of postmenopausal status before study enrollment.

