10.3.2. Contraception guidance

- Refer to Appendix Section 10.7 regarding pregnancy testing for female participants at Visit 1 (Baseline) and associated pretreatment contraception and abstinence requirements. Female participants who enter the study using contraception must continue to do so through 7 days after the last dose of study intervention.
- As described in Section 5.3, participants will be requested to abstain from sexual activity from Visit 1 (Baseline) through 7 days after the first dose of study intervention to prevent possible re-infection.

 • CONTRACEPTIVES^a ALLOWED DURING THE STUDY INCLUDE:

 • Highly Effective Methods^b That Have Low User Dependency Failure rate of <1% per year when used consistently and correctly

 • Implantable progestogen-only hormone contraception associated with inhibition of ovulation^c

 • Intrauterine device (IUD)

 • Intrauterine hormone-releasing system (IUS)^c

 • Bilateral tubal occlusion • Vasectomized partner 
 • Note: Vasectomized partner is a highly effective contraceptive method provided that the partner is the sole sexual partner of the WOCBP and the absence of sperm has been confirmed. If not, an additional highly effective method of contraception will be used. Spermatogenesis cycle is approximately 90 days. • Highly Effective Methods^b That Are User Dependent Failure rate of <1% per year when used consistently and correctly • Combined (estrogen- and progestogen-containing) hormonal contraception associated with inhibition of ovulation^c 
 • oral • intravaginal • transdermal • injectable • Progestogen-only hormone contraception associated with inhibition of ovulation^c 
 • oral • injectable • Sexual abstinence 
 • Note: Sexual abstinence is considered a highly effective method only if defined as refraining from heterosexual intercourse during the entire period of risk associated with the study intervention. The reliability of sexual abstinence needs to be evaluated in relation to the duration of the study and the preferred and usual lifestyle of the participant.

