### 6.1.3 Protocol Deviations

Important protocol deviations will be summarized.

Protocol deviations will be tracked by the study team throughout the conduct of the study in accordance with the Protocol Deviation Management Plan, entitled Study Deviation Tool and Rules. These protocol deviations will be reviewed to identify those considered as important as follows:

Data will be reviewed prior to freezing the database to ensure all important deviations, which may lead to exclusion of a participant from the analysis sets are captured and categorised in the protocol deviations dataset.

This dataset will be the basis for the summaries of important protocol deviations.

A separate participant listing of all inclusion/exclusion criteria deviations will also be provided. This listing will be based on data as recorded on the inclusion/exclusion page of the eCRF.

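### Inclusion criterion 4 ties the breastfeeding bar to childbearing potential, so a permanently sterile nursing woman meets the written entry rules despite the advice in 2.3.1

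*Protocol*

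**What the plan says.** Criterion 4 in Protocol 5.1 requires the participant to be female and then sets out one sentence on reproductive status. She may enter as a WOCBP who is shown by the predose urine test not to be pregnant. The sentence then continues "is not breastfeeding, or is not a WOCBP as defined in Appendix Section 10.3.1.2".

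The appendix referred to, 10.3.1.2, defines three classes of woman of nonchildbearing potential (WONCBP): premenarchal, permanently sterile and postmenopausal. The second is headed "Permanently sterile due to one of the following procedures", and the procedures listed are hysterectomy, bilateral oophorectomy and "Documented bilateral salpingectomy". Lactation plays no part in the definition.

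The Reproductive System Effects row of the risk table in 2.3.1 says, in its mitigation column, "Gepotidacin is not recommended in pregnant or nursing mothers". It does not limit this to women of childbearing potential. The other measures in that cell, pregnancy testing and contraception, are directed at exposure of a fetus.

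Section 5 adds that "Prospective approval of protocol deviations to recruitment and enrollment criteria, also known as protocol waivers or exemptions, is not permitted".

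**The concern.** Whether a woman is nursing has no bearing on whether she can conceive again, so childbearing potential is the wrong condition on which to hang a breastfeeding restriction. As written, criterion 4 protects the nursing infant of a fertile mother and leaves out the nursing infant of a sterile one. For that second group the eligibility rule admits a woman whom the protocol's own risk table advises against treating.

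The gap would also pass unnoticed. The SAP states in 6.1.3 that "A separate participant listing of all inclusion/exclusion criteria deviations will also be provided", built from the inclusion/exclusion page of the eCRF. A woman who breaches no entry criterion generates no entry in that listing, and the Schedule of Activities contains no lactation check that would bring her to light another way.

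**Working it through.** No sample size, power or error rate is involved, so the check is a logical one: which women does criterion 4 admit, and which would 2.3.1 advise against?

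**Inputs**
- Criterion 4, Protocol 5.1.
- WOCBP and WONCBP definitions, 10.3.1.1 and 10.3.1.2.
- Nursing statement, 2.3.1.
- Exclusion criteria 1 to 29, Protocol 5.2. All were read and none mentions breastfeeding, nursing or lactation. Exclusion 3 (sensitivity or allergy) and exclusion 6 (ability or willingness to comply) do not cover it.

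**Rules compared**
- Grouped reading of criterion 4: (WOCBP and not pregnant and not breastfeeding) or (not WOCBP).
- List reading of criterion 4: (WOCBP and not pregnant) or (not breastfeeding) or (not WOCBP).
- Position in 2.3.1: not pregnant and not breastfeeding.
- Proposed rule: not breastfeeding and [(WOCBP and not pregnant) or (not WOCBP)].

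Three yes/no attributes give eight combinations. Leaving out the two with a pregnant non-WOCBP leaves six.

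| WOCBP | Pregnant | Breastfeeding | Grouped | List | 2.3.1 | Proposed |
|---|---|---|---|---|---|---|
| yes | yes | yes | no | no | no | no |
| yes | yes | no | no | yes | no | no |
| yes | no | yes | no | yes | no | no |
| yes | no | no | yes | yes | yes | yes |
| no | no | yes | **yes** | **yes** | **no** | no |
| no | no | no | yes | yes | yes | yes |

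The grouped reading conflicts with 2.3.1 in 1 of 6 rows: breastfeeding and not a WOCBP. The list reading conflicts in 3 of 6, because it would also admit a pregnant non-nursing WOCBP and a nursing non-pregnant WOCBP. The grouped reading is plainly the sensible one, and it is the one more favourable to the plan. The fifth row fails under both. The proposed rule conflicts in 0 of 6 and, against the grouped reading, changes only that row.

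**Who is in the fifth row?** Of the three WONCBP classes, only the permanently sterile one can realistically include a nursing woman, for example after salpingectomy at delivery. A nursing woman with "Bilateral tubal occlusion" is not in it: 10.3.2 lists that as a contraceptive method and 10.3.1.2 does not list it among the sterilising procedures, so she remains a WOCBP and criterion 4 already bars her.

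**How many?** The documents give no rate. My assumption is 0, or at most 1 or 2, of about 90 enrolled: 1/90 = 1.1% and 2/90 = 2.2% as the upper range.

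**The case against.** The strongest reply has four parts.

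First, inclusion criterion 5 ties consent to the restrictions in the consent form as well as the protocol, and the consent pages are not in the text supplied. The form may address nursing. That cannot be checked, so the finding is confined to the written protocol criteria. Even so, criterion 5 is framed around the capacity to give consent, and it is not a substitute for a stated eligibility condition.

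Second, the ban on waivers stops sites admitting women who fail a criterion; it does not oblige them to enrol everyone who passes. This is correct. An investigator who has read 2.3.1 can decline to enrol a nursing woman without any waiver. The point that remains is narrower: nothing in the criteria tells the investigator to decline her.

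Third, the wording in 2.3.1 is advisory, and silence about a rare subgroup is not an instruction to enrol it. This is also fair as far as it goes, but the protocol already treats the same advice as an entry bar for fertile women and gives no reason to treat sterile women differently.

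Fourth, the sponsor probably meant the bar to cover all women, and six combinations counted equally say nothing about frequency. Both are true. Probable intent is a reason to correct the sentence, and the count shows only where the rule fails, not how often.

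**Conclusion.** The point holds and is minor. On either reading of the sentence, a permanently sterile woman who is breastfeeding meets criterion 4, and no exclusion criterion stops her, although 2.3.1 advises against treating nursing mothers. On the sensible reading the defect is confined to that one group, and other nursing women are already barred.

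The expected number affected is very small, plausibly none; this rests on assumption, since the documents give no rate. Sample size, estimand and analysis do not change. What is at stake is the exposure of a nursing infant, through an operative entry rule that gives the wrong answer if followed as written. The conclusion is limited to the protocol criteria, because the consent form could not be seen.

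**What to change.** Take the breastfeeding condition out of the WOCBP branch and make it a requirement for every participant. Criterion 4 could read, in substance: the participant is not breastfeeding, whatever her childbearing class; and she is either (a) a WOCBP with a negative high-sensitivity urine pregnancy test before the first dose at baseline, or (b) not a WOCBP under 10.3.1.2.

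The change moves one existing phrase. It needs no new procedure or assessment and no new data item, and its effect on recruitment would be negligible. No change to the SAP is needed: a nursing participant enrolled in error would then be an eligibility deviation and would fall within the listing already planned in SAP 6.1.3.

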5.2. Exclusion criteria

Participants are excluded from the study if any of the following criteria apply:

Medical conditions and history

1. The participant resides in a nursing home or dependent care type-facility.
2. The participant has a body mass index $\geq 40.0 \text{ kg/m}^2$ or a body mass index $\geq 35.0 \text{ kg/m}^2$ and is experiencing obesity-related health conditions such as uncontrolled high blood pressure or uncontrolled diabetes.
3. The participant has a history of sensitivity to the study intervention, or components thereof, or a history of a drug or other allergy that, in the opinion of the investigator or medical monitor, contraindicates study participation.
4. The participant is immunocompromised or has altered immune defenses that may predispose the participant to a higher risk of treatment failure and/or complications (e.g., uncontrolled diabetes in the judgment of the investigator, renal transplant recipients, participants with clinically significant persistent granulocytopenia [absolute neutrophil count $< 1000/\mu\text{L}$], and participants receiving immunosuppressive therapy, including corticosteroid therapy [$> 40 \text{ mg/day}$ prednisolone or equivalent for $> 1 \text{ week}$, $\geq 20 \text{ mg/day}$ prednisolone or equivalent for $> 2 \text{ weeks}$, or prednisolone or equivalent $\geq 10 \text{ mg/day}$ for $> 6 \text{ weeks}$]). Participants with a known CD4 count of $< 200 \text{ cells/mm}^3$ are to not be enrolled.
5. The participant has any of the following:
 - Medical condition that requires medication that may be impacted by inhibition of acetylcholinesterase, such as:
 - Poorly controlled asthma or chronic obstructive pulmonary disease at baseline and, in the opinion of the investigator, not stable on current therapy
 - Acute severe pain, uncontrolled with conventional medical management
 - Active peptic ulcer disease
 - Parkinson disease
 - Myasthenia gravis
 - A history of seizure disorder requiring medications for control (this does not include a history of childhood febrile seizures)

OR

- Any surgical or medical condition (active or chronic) that may interfere with drug absorption, distribution, metabolism, or excretion of the study intervention (e.g., ileostomy or malabsorption syndrome).
6. The participant, in the judgment of the investigator, would not be able or willing to comply with the protocol or complete study follow-up.

7. The participant has a serious underlying disease that could be imminently life-threatening, or the participant is unlikely to survive for the duration of the study period.

Urinary tract infection/renal/urogenital exclusions

8. The participant has uUTI that is known or suspected to be due to fungal, parasitic, or viral pathogens; or known or suspected to be due to *Pseudomonas aeruginosa* or Enterobacteriales (other than *E. coli*) as the contributing pathogen.
9. The participant has symptoms known or suspected to be caused by another disease process, such as overactive bladder, chronic incontinence, or chronic interstitial cystitis, that may interfere with the clinical efficacy assessments or preclude complete resolution of uUTI symptoms.
10. The participant has an anatomical or physiological anomaly that predisposes the participant to UTIs or may be a source of persistent bacterial colonization, including calculi, obstruction or stricture of the urinary tract, primary renal disease (e.g., polycystic renal disease), or neurogenic bladder, or the participant has a history of anatomical or functional abnormalities of the urinary tract (e.g., chronic vesico-ureteral reflux, detrusor insufficiency).
11. The participant has an indwelling catheter, nephrostomy, ureter stent, or other foreign material in the urinary tract.
12. The participant, in the opinion of the investigator, has an otherwise complicated UTI, an active upper UTI (e.g., pyelonephritis, urosepsis), signs and symptom onset ≥ 96 hours before study entry, or a temperature $\geq 101.4^{\circ}\text{F}$ ($\geq 38^{\circ}\text{C}$), flank pain, chills, or any other manifestations suggestive of upper UTI.
13. The participant has known anuria, oliguria, or significant impairment of renal function (creatinine clearance <30 mL/min or clinically significant elevated serum creatinine as determined by the investigator).
14. The participant presents with vaginal discharge at Baseline (e.g., suspected sexually transmitted disease).

Cardiac exclusions

15. The participant has congenital long QT syndrome or known prolongation of the QTc interval.
16. The participant has uncompensated heart failure.
17. The participant has severe left ventricular hypertrophy.
18. The participant has a family history of QT prolongation or sudden death.
19. The participant has a recent history of vasovagal syncope or episodes of symptomatic bradycardia or brady arrhythmia within the last 12 months.
20. The participant is taking QT-prolonging drugs or drugs known to increase the risk of TdP per the www.crediblemeds.org. “Known Risk of TdP” category at the time of her Baseline Visit, which cannot be safely discontinued from the Baseline Visit (Day 1) through 7 days after the first dose of study intervention; or the participant is taking a strong CYP3A4 inhibitor or a strong P-gp inhibitor.

Cardiac electrocardiogram exclusions

21. The participant has a mean triplicate QTc >450 msec or a mean triplicate QTc >480 msec for participants with bundle-branch block.

Note:

- The QTc is the QT interval corrected for heart rate according to QTcB, QTcF formula, and/or another method. It is either machine read or manually overread.
- The specific formula used to determine eligibility and discontinuation for an individual participant is to be determined prior to initiation of the study. In other words, several different formulas cannot be used to calculate the QTc for an individual participant and then the lowest QTc value used to include or discontinue the participant from the trial.

22. The participant has a documented or recent history of uncorrected hypokalemia within the past 3 months.

Hepatic exclusions

23. The participant has a known ALT value $>2 \times$ ULN.
24. The participant has a known bilirubin value $>1.5 \times$ ULN (isolated bilirubin $>1.5 \times$ ULN is acceptable if bilirubin is fractionated and direct bilirubin $<35\%$).
25. The participant has a current or chronic history of liver disease or known hepatic or biliary abnormalities (with the exception of Gilbert's syndrome or asymptomatic gallstones), including symptomatic viral hepatitis or moderate-to-severe liver insufficiency (Child Pugh class B or C).

Note: Participants with asymptomatic viral hepatitis are eligible for study participation.

Prior antibiotic/antifungal use exclusion

26. The participant has received treatment with other systemic antimicrobials or systemic antifungals within 1 week before study entry.

Concomitant medication use exclusion

27. The participant plans to use any of the prohibited medications or nondrug therapies from the Baseline Visit through 7 days after the first dose of study intervention as detailed in Section 6.9.

Prior/concurrent clinical study experience

28. The participant has been previously enrolled in this study or has previously been treated with gepotidacin.
29. The participant has participated in a clinical trial and has received an investigational product within 30 days or 5 half-lives, whichever is longer.

